### 3.1 Study population

Participants will be recruited through referrals to our treatment clinic. We will recruit 30 outpatients 18 to 65 years of age with a diagnosis of unipolar MDD according to Diagnostic and Statistical Manual of Mental Disorders, fifth edition (DSM-5) criteria and confirmed by psychiatrists by means of the Mini-International Neuropsychiatric Interview (MINI) with a score of at least 17 on the 17-item Hamilton Depression Rating Scale (HRSD-17) as well as a low risk of suicide (Blumberger et al. 2018). Participants will be required to have had no increase or initiation of any psychotropic medication in the 4 weeks prior to screening and have normal blood work (thyroid, complete blood count, electrolytes) in the past 6 months. Exclusion criteria will be bipolar disorder, substance use disorder within the last 3 months, dementia, personality disorder, brain injury, pregnancy, specific contraindications to tDCS (e.g., intracranial implants) or previous tDCS treatment. Antidepressant use will be permitted, but anticonvulsant medication or benzodiazepine use of more than 2 mg lorazepam equivalent will not be allowed.

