### 3.3 Outcomes

Participants will be initially assessed at baseline one week before treatment, on every treatment day, at the end of the last treatment day, and one and four weeks following treatment. The complete schedule is presented in **Fig. 2-3**.

**Primary objective:** participants will be systematically assessed every day of treatment and at follow-ups for potential AEs, and all AEs will be reported. At each treatment sessions, a safety check (i.e., visual skin examination) will be performed before and after each tDCS session, and pain levels will be assessed using a Verbal Rating Scale (VRS) of 0 to 10 (10 being the maximally tolerable amount of pain) (**Fig. 4**). Cognitive safety will also be assessed pre- and post-treatment using various tests, such as the Rey Auditory Verbal Learning Test, Rey-Osterrieth Complex Figure, Trail Making Test Parts A & B and verbal fluency test (Fig. 3). Completion and retention rates as well as the number of treatment sessions completed will be assessed. The following data will also be collected: number of potential participants referred to the study, number of patients screened, number of potential participants considered eligible, number of participants recruited, number of participants who initiated the intervention, number of treatment sessions completed, dropout rates and number of participants who completed treatment and assessments. Information on attendance in the intervention will also be measured. Regarding the **secondary objective**, depressive symptoms changes will be assessed through the HRSD-17, Montgomery-Asberg Depression Rating Scale (MADRS), Patient Health Questionnaire-9 (PHQ-9) and General Anxiety Disorder-7 (GAD-7) (Fig. 3). We will also use the 6-item HRSD (Fig. 3) before every treatment day and at the end of the last day, which is a highly sensitive depression scale that can be administered daily during treatment (22).

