### 3.5 Statistical analysis

Inferential statistics will be performed on baseline characteristics utilizing independent samples t-tests (two-tailed) for continuous variables and Chi-square tests for categorical variables and to summarise rates of consent, study retention, as well as data quality (completion of outcome measures and missing data). Treatment safety will be assessed by a line listing, frequency tabulations and 95% confidence intervals. We will also perform repeated measures analyses of variance (ANOVA) on mood scales score at different timepoints to assess the effect of the treatment through time. Planned repeated contrasts will be used to make comparisons between the different evaluation times. To evaluate cognitive safety of the treatment in patients, we will use the reliable change index methodology to differentiate the possible effect of the treatment on cognitive functions and outcome results due to practice effects.

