Considering that very little data is available regarding intensive tDCS treatments, participants will be monitored by a dermatologist. An initial consultation will take place before the start of the treatment (Visite 2) and patients will be reassessed at the end of treatment session (visite 13). During the treatment week, high-resolution photographs of the skin will be taken daily before and after treatments and shared with the dermatologist, who will assess the treatment sites for skin lesions using a a global rating scale (0:absent to 3: severe). The dermatologist will advise the treatment team to continue or to stop treatment.

Common side effects are expected and will be recorded separately from AEs. Participants will be asked to defer any medication changes for 4 weeks before and during the course of treatment to avoid confounding effects. All AEs reported during the study will be recorded in patients' research file and include the following information: description and nature of event, onset time and date, duration, intensity, seriousness, relationship to treatment, action taken and evolution. In case of a serious adverse event, the aforementioned information will be collected in detail and will be reported to the CHUM IRB. Any AEs deemed to be related to the study by the Primary Investigator (PI), or that result in a participant's withdrawal from the study, will be followed until its resolution or until the patient is considered stable. The decision as to whether or not an AE is sufficiently severe to warrant the termination of patient treatment will be left to the clinical judgment of the (PI). A participant may also voluntarily withdraw from treatment due to what he/she perceives as an intolerable AE. If either of these occurs, the participant will be required to undergo an end-of-study assessment and will be offered appropriate care under medical supervision until the condition becomes stable.

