### **3.7 Attendance and Withdrawal Criteria**

Participants will be encouraged to attend all scheduled treatments. Those that do not meet the following criteria will be excluded from the per protocol analysis if they:

- (1) Miss / Fail to attend more than 2 treatment days in the course overall.
- (2) Miss / Fail to attend more than 10 treatment sessions overall.
- (3) Cannot tolerate stimulation
- (4) Change their regimen of psychotropics during the treatment period.
- (5) Withdraw consent to participate.

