## **4.0 SUBJECT INCLUSION/EXCLUSION**

### **4.1 Inclusion Criteria**

#### **4.1 Inclusion Criteria**

Patients will be included if they:

- (1) are outpatients
- (2) are voluntary and competent to consent to treatment
- (3) have a Mini-International Neuropsychiatric Interview (MINI) confirmed diagnosis of MDD, single or recurrent
- (4) are between the ages of 18 and 65
- (5) have a score  $\geq 17$  on the HRSD-17 item
- (6) have had no increase or initiation of any psychotropic medication in the 4 weeks prior to screening
- (7) able to adhere to the treatment schedule
- (8) have normal blood work (thyroid, complete blood count, electrolytes)

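### The limits on medication changes end with treatment, so drug changes made afterwards can bias the follow-up mood results, mainly at week 4

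*Combined protocol and SAP*

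**What the plan says.** The combined protocol and SAP has three rules on medication change.

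- **Entry (3.1 and 4.1, criterion 6).** Participants must "have had no increase or initiation of any psychotropic medication in the 4 weeks prior to screening". Stable background treatment is allowed: "Antidepressant use will be permitted".
- **Request to participants (3.6).** "Participants will be asked to defer any medication changes for 4 weeks before and during the course of treatment to avoid confounding effects".
- **Per-protocol exclusion (3.7, item 4).** A participant leaves the per-protocol analysis if they "Change their regimen of psychotropics during the treatment period".

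After a baseline visit, section 3.3 places assessments "on every treatment day, at the end of the last treatment day, and one and four weeks following treatment". Section 3.5 plans "repeated measures analyses of variance (ANOVA) on mood scales score at different timepoints to assess the effect of the treatment through time", with contrasts between evaluation times. It names no medication covariate, no rule for scores obtained after a drug change, and no sensitivity analysis.

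For comparison, exclusion criterion (11) in 4.2 asks that psychotherapy be expected to stay stable for the whole study. Medication has no matching rule.

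**The concern.** Section 3.6 gives confounding as the reason for holding medication steady, so the plan itself accepts that drug changes can distort the mood scores. The protection ends on the last treatment day, but two assessments come after it. Participants have also been asked to put off changes until then, which makes the follow-up weeks a natural time for changes to happen.

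Someone who starts an antidepressant the day after the last session stays in the per-protocol set. Their week-4 score enters the analysis as it stands. With one arm and no control, no comparison group shares the drug effect. If the people who change are mainly non-responders, their later improvement would read as a lasting or delayed effect of tDCS. At stake is what the pilot can say about durability, which a later randomized trial might draw on.

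**Working it through.** **Step 1. Set the time windows side by side.**

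| Period | Entry (3.1, 4.1) | Request (3.6) | Per-protocol (3.7(4)) | Mood assessed (3.3) |
|---|---|---|---|---|
| 4 weeks before screening | Increase or initiation of psychotropics barred | Covered only where it overlaps the 4 weeks before treatment | No | No |
| Screening to first treatment | No | Any medication change, within 4 weeks of treatment | No | Baseline |
| Treatment | No | Any medication change | Psychotropic regimen change | Daily and end of last day |
| After treatment, to week 4 | No | No | No | Weeks 1 and 4 |

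The last row is the gap: two assessments and no medication rule. Section 3.5 says only that different timepoints are analysed. That weeks 1 and 4 are among them is inferred from 3.3.

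**Step 2. Size in HRSD-17 points.** The plan gives no figure to reproduce and no rate of medication change. Let q be the share who change a drug after treatment and g the mean gain from it by week 4.

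Bias in mean week-4 improvement = q × g.

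- Low: 0.10 × 3 = 0.3 points.
- High: 0.30 × 6 = 1.8 points.

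Both inputs are assumptions. Week 1 is less exposed, because changes have had less time to be made or to act.

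**Step 3. Size against the effect in 3.4.** With q = 10-40% and an added gain e = 0.2-0.5 SD (also assumed), the shift is 0.10 × 0.2 = 0.02 SD to 0.40 × 0.5 = 0.20 SD. Against the effect size of 0.5 used in 3.4, that is 0.02/0.5 = 4% to 0.20/0.5 = 40%.

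A simulation of a one-sample t-test from end of treatment to week 4 (30 patients, no true change after treatment, e = 0.3-0.5 SD, 40,000 runs, nominal two-sided 5%) gave these rejection rates:

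- q = 10%: about 5.5-6%.
- q = 20%: about 6-8%.
- q = 40%: about 10-18%.

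**Step 4. Does removing the affected scores help?** That depends on the model. A standard repeated-measures ANOVA drops anyone with a missing score, so it loses the changers at every timepoint. Suppose 70% improve by 10 points, 30% would improve by 3 without a drug, and those 30% start a drug worth 6 points:

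- Target mean without drug: 0.7 × 10 + 0.3 × 3 = 7.9.
- All scores: 0.7 × 10 + 0.3 × (3 + 6) = 9.7, bias +1.8.
- Changers dropped: 10.0, bias +2.1.

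In a simulation with 10-30% changing, gains of 3-6 points and the chance of a change driven by the end-of-treatment score, the bias was 0.3-1.8 points with all scores and 0.4-1.0 with changers dropped. It was about 0 in a likelihood-based model that keeps the changers' earlier scores. The middle figure depends on the assumed spread and correlation of scores. The last holds because the simulated changes depended only on scores the model used.

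**Step 5. The pre-treatment rules.** Entry covers increases and initiations of psychotropics, counted back from screening. Section 3.6 covers any medication change, counted back from treatment. A dose reduction or stop shortly before screening therefore meets the entry criterion, yet it can fall inside the window in 3.6 if treatment follows soon after. This affects stability at baseline. It has no part in steps 2 to 4.

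**The case against.** The strongest case against runs as follows. The primary objective is safety, tolerability and feasibility, and the mood data are secondary and preliminary. With no control arm, no timepoint isolates a tDCS effect, whatever happens to medication. A contrast from baseline to the end of treatment, if made, is untouched by later drug changes. The size is one assumption multiplied by another, and at 10-20% changing the rejection rate barely moves. The three rules serve different purposes (eligibility, a request, an analysis set) and can all be followed at once.

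Much of this stands. It limits the point to the follow-up mood results and to a modest correction. It does not remove the gap: the plan schedules a week-4 assessment, and gives a reader no means to tell a lasting response from a new prescription.

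A reader might also infer four stronger things that the documents do not support:

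- **That the mismatch with the entry criterion causes the week-4 problem.** It concerns the time before treatment and is a separate matter.
- **That the follow-up results will be inflated.** Stopping or reducing a drug after treatment could worsen scores, and the rate of change is unknown.
- **That medication is not recorded at follow-up.** The schedule figures are not visible in the text reviewed, so this cannot be checked.
- **That the analysis needs a different principal timepoint.** That is a preference. Section 3.3 explicitly ties only the 6-item HRSD to the end of the last day, so HRSD-17 at that visit cannot be confirmed.

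**Conclusion.** The point holds for the follow-up mood results. The plan limits medication changes to avoid confounding, ends the limit with treatment, keeps measuring mood for four weeks, and says nothing about how later changes are handled. Week 4 is the more exposed visit. The likely direction is towards apparent durability, on the assumption that non-responders are the ones who start drugs. The size cannot be settled from the documents: 0.3-1.8 HRSD-17 points under the assumed 10-30% changing and 3-6 points gained, so it may be small or material. The safety and feasibility outcomes are little affected.

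The difference between 3.6 and the entry criterion is a second, smaller finding about baseline stability. Its effect has not been quantified. Overall this is worth correcting because the correction is cheap; it does not threaten the study's main purpose.

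**What to change.** No change to care is proposed.

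1. **Record.** Capture every psychotropic change (start, stop, increase, reduction, with date) through week 4 at the existing visits, if the schedule does not already provide for it. Report the number of participants affected by visit.
2. **Analyse (3.5).** State that weeks 1 and 4 are included. Report them using all scores, and again with scores after a psychotropic change set to missing. Fit the second analysis as a likelihood-based mixed model that keeps those participants' earlier scores, not as a repeated-measures ANOVA that drops them.
3. **Reconcile.** Bring the medication windows in 3.1, 3.6, 3.7(4) and 4.1 criterion (6) into agreement on which changes count and from which date. Which rule to adopt is for the investigator.

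The cost is at most one case report form field at two existing visits, one extra model and a wording amendment. The downside is a less precise week-4 estimate in the sensitivity analysis, which rests on a missing-at-random assumption. That is more plausible if the model includes an end-of-treatment score on the same scale, so the sponsor should confirm which scales are collected then.

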### **3.7 Attendance and Withdrawal Criteria**

Participants will be encouraged to attend all scheduled treatments. Those that do not meet the following criteria will be excluded from the per protocol analysis if they:

- (1) Miss / Fail to attend more than 2 treatment days in the course overall.
- (2) Miss / Fail to attend more than 10 treatment sessions overall.
- (3) Cannot tolerate stimulation
- (4) Change their regimen of psychotropics during the treatment period.
- (5) Withdraw consent to participate.

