## 2.0 STUDY OBJECTIVES

Primary objective: To assess the safety, tolerability, and feasibility of an intensive tDCS protocol for MDD. We hypothesize that our intensive tDCS protocol will be safe, well-tolerated and feasible.

Secondary objective: To gather preliminary data on the clinical effects of the protocol.

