### 3.2 Intervention

Treatments will take place over 10 days (Monday to Friday). Participants will receive 5 tDCS sessions each day, for a total of 50 sessions. Each tDCS session will last 20 min at a 2 milliamps intensity and will be spaced by 20 min intervals (3h treatment block). tDCS sessions will be administered through 1x1 tES mini-CT devices (Soterix, New York, USA) already acquired by the clinic (Fig. 1). These devices have been used in several large MDD trials and are Health Canada approved. They are equipped with a "SNAPstrap" fixing system to reliably position the two (2) electrodes (anode and cathode). The electrodes will be placed on the scalp according to the EEG 10-20 system, with the anode in F3 and the cathode in F4. Treatment will be administered by trained research personnel and single-use "SNAPpads" pre-saturated electrodes

will be provided to participants for each treatment. These electrodes contain just the right amount of saline solution to minimize any cutaneous side-effects.

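### The mood-scale ANOVA in section 3.5 has no analysis set and no missing-data method, so in its standard form it would rest on people who attended every assessment

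*Combined protocol and SAP*

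**What the plan says.** Section 3.5 (Statistical analysis) applies repeated-measures ANOVA, with repeated contrasts, to the mood scales at timepoints it does not list. It mentions missing data only as an aspect of data quality to be summarised. It states no population for any analysis.

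Section 3.7 (Attendance and Withdrawal Criteria) names the protocol's only analysis set: "Those that do not meet the following criteria will be excluded from the per protocol analysis if they". Read literally, that stem contradicts itself; the list makes sense only as reasons for exclusion. Reason (1) reads "Miss / Fail to attend more than 2 treatment days in the course overall". Reason (2) sets the matching limit of 10 missed sessions, and reason (3) is worded "Cannot tolerate stimulation". Reason (4) is an altered psychotropic regimen while on treatment, and reason (5) is withdrawal of consent. No section says which analyses use this set or what it is to be compared with.

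Section 3.3 (Outcomes) places the HRSD-6 ahead of each treatment day and once more when the final day closes. It also lists the HRSD-17, MADRS, PHQ-9 and GAD-7. For the primary objective it states that "all AEs will be reported" and lists the "number of participants who initiated the intervention, number of treatment sessions completed, dropout rates and number of participants who completed treatment and assessments". Section 3.6 requires an end-of-study assessment when treatment stops because of an adverse event.

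**The concern.** Two filters can act on the mood analysis, and neither is ruled out. The first is the per-protocol set. With no other set named, it is the one an analyst would find in the document, and it removes people who did not tolerate the treatment, attended poorly or left. The second is the ANOVA itself, which in its standard form keeps only participants with a score at every timepoint in the model.

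The filters do not coincide. A participant may miss one or two treatment days and remain per protocol, yet be dropped from an ANOVA of the daily HRSD-6 scores if the ratings for those days are not obtained another way.

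People who stop or skip treatment may well differ in mood course from those who finish, so the reported change could look better than it was among all who were treated. With no set fixed in advance, the choice can also be made after the scores are seen. The mood data are secondary and preliminary, but section 8.0 presents this study as a possible step towards a large randomised trial, and these results could feed into it.

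**Working it through.** **Inputs from the protocol.** 30 participants (3.4); 10 treatment days (3.2: "Treatments will take place over 10 days (Monday to Friday") with 5 sessions a day, 50 in total; the exclusion limits in 3.7. The protocol gives no rate of missing scores. Section 3.4 gives a required number of 24, raised to 30 for dropouts, which implies 1 − 24/30 = 20%. The 24 cannot be reproduced because significance level, sidedness and power are not stated. It serves below only as a benchmark.

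**Do the two filters agree?** Missing 2 whole days means missing 2 × 5 = 10 sessions. That is not more than 2 days and not more than 10 sessions, so the participant stays per protocol.
- HRSD-6 assessments: 10 before treatment days + 1 at the end = 11.
- If the ratings on the 2 missed days are lost, 11 − 2 = 9 scores remain.
- A complete-case ANOVA of the 11 scores uses none of those 9; a mixed model uses all of them.

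**Expected complete cases.** Assume each assessment is missed independently with probability p. With m assessments, the expected number complete is 30 × (1 − p)^m. If the first is always observed, it is 30 × (1 − p)^(m − 1). The 4-visit layout (baseline, end of treatment, 1 week, 4 weeks) is assumed, because the schedule figure is not shown.

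| p (assumed) | 11 HRSD-6 scores | 11, first always observed | 4 visits | 4, first always observed |
|---|---|---|---|---|
| 1% | 30 × 0.8953 = 26.9 | 27.1 | 28.8 | 29.1 |
| 2% | 30 × 0.8007 = 24.0 | 24.5 | 27.7 | 28.2 |
| 5% | 30 × 0.5688 = 17.1 | 18.0 | 24.4 | 25.7 |

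At about 2% missing per assessment, an 11-point analysis is already down to about the 24 that section 3.4 calls for.

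**Effect of clustering.** At 2%, the expected number of missed scores is 30 × 11 × 0.02 = 6.6. Spread independently, they cost 30 − 24.0 = 6.0 participants. If each affected person missed two, they would cost 6.6/2 = 3.3. The table therefore leans towards the larger loss.

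**Size of the covariance model.** An unstructured matrix for m timepoints has m(m + 1)/2 parameters: 4 × 5/2 = 10 for 4 visits and 11 × 12/2 = 66 for the daily HRSD-6. With 30 participants the first is workable and the second is not.

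**The case against.** **The primary outcomes are not tied to the per-protocol set.** Because the primary objective is "To assess the safety, tolerability, and feasibility of an intensive tDCS protocol for MDD", a reader might infer that tolerability and attendance will be computed per protocol, making tolerability 100% and attendance at least 40 of 50 sessions by definition. The documents do not support that. Section 3.3 promises to report every adverse event. It lists sessions completed in the same sentence as referral, screening, recruitment and dropout counts, which points to full denominators. Section 3.5 summarises consent and retention. No section defines a proportion tolerating treatment; inability to tolerate stimulation appears only as an exclusion reason. This objection stands, and the point is limited accordingly.

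**Per protocol may be one analysis among several.** The wording of 3.7 allows this, since it excludes people from that analysis and not from the study. But no other set is described, so the mood analysis still has none.

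**An 11-point ANOVA is only one reading.** Section 3.5 does not say that all daily HRSD-6 scores enter one model. That is correct. For the assumed 4-visit scales with the first score observed, the loss at 1% to 5% is about 1 to 4 people (30 − 29.1 to 30 − 25.7). The gap remains, but it is smaller.

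**Early stoppers are assessed.** This applies only to stops caused by adverse events. The text does not show whether mood scales are included, and no rule says how such scores are analysed.

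**Conclusion.** The point holds for the mood scales. Section 3.5 fixes neither the set nor the handling of missing scores, and the stated method in its standard form is complete-case. The results could describe mainly people who tolerated and completed the course. The direction of bias is likely favourable but cannot be established from the documents.

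The size depends on assumed missingness: at 1% to 5% per assessment, roughly 3 to 13 of 30 participants are lost from an 11-point HRSD-6 analysis and roughly 1 to 6 from a 4-visit scale, with fewer lost under clustering. The larger range also requires that the daily scores be analysed together and that missed days leave missing ratings.

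The point does not extend to a claim that the primary safety, retention or session counts will be biased. For those, naming the set confirms what is probably already intended. This is a worthwhile correction to make before analysis; it does not undermine the study.

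**What to change.** In section 3.5:

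- **(a) Mood scales.** Analyse all participants who started at least one tDCS session. Replace the ANOVA with a likelihood-based mixed model for repeated measures that uses every available score.
  - For scales with few visits, use an unstructured covariance with a small-sample degrees-of-freedom correction.
  - For the daily HRSD-6, use a parsimonious structure based on actual assessment time, such as a random intercept and slope or a continuous-time correlation, again with a small-sample correction. A structure that treats ratings as equally spaced would not fit: there is a weekend gap, and two ratings fall on the last day.
  - State the missing-at-random assumption, report the number contributing at each visit, and enter early stoppers' end-of-study mood scores at their actual time where these were collected.
- **(b) Other outcomes.** Name the same treated set for safety, session counts and cognition. Report how many participants lack a post-treatment cognitive test, because the reliable change index needs both pre and post scores.
- **(c) Per protocol.** Keep it only as a labelled sensitivity analysis of the mood scales. Report the numbers excluded for reasons (1), (2), (3) and (5) as feasibility or tolerability results.

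The cost is revised wording and slightly more analysis work, with no new participants or visits. The model relies on missing at random, which cannot be verified from the data, and the figures may be less favourable. Scores may still be missing for people lost through non-attendance or withdrawal of consent.
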